7.3.2 Safety Analyses

Adverse events will be coded by preferred term and system organ class using the latest version of the Medical Dictionary for Regulatory Activities. All AE data will be presented in a data listing. Treatment-emergent AEs will be summarized by hepatic condition and overall, as well as by severity and relationship to study drug. Serious AEs and AEs leading to early discontinuation will also be presented in data listings.

Actual values and changes from baseline for clinical laboratory test results, vital sign measurements, and 12-lead ECG results will be summarized by hepatic condition at each time point using descriptive statistics (number of subjects, mean, SD, minimum, median, and maximum). Shift tables will be generated for clinical laboratory test results. Clinical laboratory test results, vital sign measurements, 12-lead ECG results, and physical examination findings will be presented in data listings.

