In Part 2, a cohort of at least 8 subjects comprising of mild and moderate or moderate and severe hepatic impairment subjects will be administered aramchol as multiple doses to obtain the PK profile of aramchol at steady state. A decision on the severity of hepatic impairment of subjects to participate in Part 2 (multiple-dose) will be made by the sponsor based on the available safety and PK results from Part 1 (single-dose).

Healthy control subjects will be matched with the hepatically impaired subjects according to gender, age (± 10 years), and BMI ($\pm 20\%$).

Single Dose (Part 1):

On Day 1, subjects will receive a single oral dose of 600 mg aramchol administered with 240 mL of water in the morning, after an overnight fast of at least 10 hours, and approximately 30 minutes after consuming a standardized breakfast. Subjects will remain fasted except for water for 2 hours after dosing. During the study, subjects may consume water on an ad libitum basis. Hepatically impaired subjects will receive a diet standardized for hepatic impairment and healthy control subjects will receive a similar diet.

Serial blood samples for PK analysis of aramchol concentrations in plasma will be collected before dosing (0 hour) and up to 168 hours for healthy subjects and 240 hours for hepatically impaired subjects after administration of aramchol.

Subjects will be confined to the clinical site from Day -1 until discharge on Day 8 for healthy control subjects and on Day 11 for hepatically impaired subjects. The duration of the study, excluding screening, is approximately 23 days.

Multiple Dose (Part 2):

Multiple dosing will involve twice daily (approximately 12 hours apart) oral administration of aramchol for 11 days with a single AM dose on Day 12 to achieve steady state. The dosage will not exceed 300 mg twice daily but may be adjusted to give lower exposure depending on review of available data on any reduction in clearance associated with hepatic impairment seen with single doses in Part 1. Subjects will consume a standardized meal 30 minutes prior to the AM and PM doses of aramchol. Subjects will remain fasted except for water for 2 hours after dosing. During the study, subjects may consume water on an ad libitum basis. Hepatically impaired subjects will receive a diet standardized for hepatic impairment and healthy control subjects will receive a similar diet.

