3.1 SCHEDULE OF EVENTS - SINGLE DOSE ARAMCHOL (PART 1)

Procedure ^(a)	Phase Day	Screening	Check-in	Treatment Period										EOS	
		-28 to -2	-1	1	2	3	4	5	6	7	8	9	11	22 (±2)	
Admission to clinic			X												
Discharge from clinic											X ^(b)		X ^(c)		
Outpatient visit ^(d)														X	
Informed consent		X													
Demographics		X													
Serology ^(e)		X													
Serum FSH ^(f)		X													
Inclusion/exclusion criteria		X	X												
Medical history		X	X												
Height, weight, and BMI ^(g)		X	X											X	
Physical examination ^(h)		X	X											X	
Vital sign measurements ⁽ⁱ⁾		X	X	X	X	X	X				X ^(j)		X ^(k)	X	
12-lead ECG ^(l)		X	X	X	X		X				X ^(j)		X ^(k)	X	
Clinical laboratory testing ^(m)		X	X				X				X ^(j)		X ^(k)	X	
Urine drug/alcohol screen ⁽ⁿ⁾		X	X												
Urine pregnancy test ^(o)		X	X											X	
Aramchol administration ^(p)				X											
PK blood sample collection ^(q)				X	X	X	X	X	X	X	X	X ^(k)	X ^(k)		
Adverse events ^(t)		← X →													
Prior/concomitant medications		← X →													

Abbreviations: AE, adverse event; BMI, body mass index; ECG, electrocardiogram; EOS, end of study; FSH, follicle-stimulating hormone; PK, pharmacokinetic.

Notes:

- (a) When procedures overlap or occur at the same time point, all blood draws should follow vital sign measurements or ECGs, and PK sampling should be timed to occur last and as close to the scheduled time window as possible.
- (b) Discharge following all study procedures on Day 8 for healthy control subjects.
- (c) Discharge following all study procedures on Day 11 for hepatically impaired subjects.
- (d) An EOS visit will occur 11 days after the Day 11 (240-hour) PK blood sample.
- (e) A complete list of serology assessments is provided in Section 6.2.2.
- (f) Females only. Further details are provided in Section 6.2.2.
- (g) Height and weight will be measured and BMI will be calculated at screening only. Only weight will be measured at check-in and EOS.
- (h) A full physical examination will be performed at screening. A brief physical examination will be performed at check-in and EOS. Further details are provided in Section 6.2.5.
- (i) Further details on vital sign measurements are provided in Section 6.2.3.
- (j) Collected for healthy control subjects only.

- (k) Collected for hepatically impaired subjects only.
- (l) Further details on ECG recordings are provided in Section 6.2.4.

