6.2.1 Adverse Events

Adverse events will be assessed from the time the subject signs the ICF until EOS and should be followed until they are resolved, stable, or judged by the investigator to be not clinically significant.

The investigator is responsible for ensuring that all AEs and SAEs are recorded in the eCRF and SAEs are reported to the sponsor, regardless of their relationship to study drug or clinical significance. If there is any doubt as to whether a clinical observation is an AE, the event should be reported.

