6.2.1.1 Adverse Event Definitions

An AE is defined as any untoward medical occurrence associated with the use of a drug in humans, whether or not considered drug related. Subjects will be instructed to contact the investigator at any time after signing the ICF if any symptoms develop.

A treatment-emergent AE is defined as any event not present before exposure to study drug or any event already present that worsens in intensity or frequency after exposure.

A suspected adverse reaction is any AE for which there is a reasonable possibility that the study drug caused the AE. For the purposes of investigational new drug safety reporting, “reasonable possibility” means that there is evidence to suggest a causal relationship between the study drug and the AE. A suspected adverse reaction implies a lesser degree of certainty about causality than an adverse reaction.

An adverse reaction is any AE caused by a study drug. Adverse reactions belong to a subset of all suspected adverse reactions and indicate that there are reasons to conclude that the study drug caused the event.

An AE or suspected adverse reaction is considered “unexpected” if it is not listed in the investigator’s brochure or if it occurs with specificity or severity that has not been previously observed with the study drug being tested.

An AE or suspected adverse reaction is considered an SAE/suspected unexpected serious adverse reaction if, in the view of either the investigator or sponsor, it results in any of the following outcomes:

- Death
- Life-threatening AE
- Inpatient hospitalization or prolongation of existing hospitalization
- Persistent or significant incapacity or substantial disruption of the ability to conduct normal life functions
- Congenital anomaly or birth defect

Important medical events that may not result in death, be life threatening, or require hospitalization may be considered serious when, based upon appropriate medical judgment, they may jeopardize the subject and may require medical or surgical intervention to prevent

one of the outcomes listed in this definition. Examples of such medical events include allergic bronchospasm requiring intensive treatment in an emergency room or at home, blood dyscrasias or convulsions that do not result in inpatient hospitalization, or the development of drug dependency or drug abuse.

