6.2.1.2 Eliciting and Documenting Adverse Events

Subjects will be asked a standard question to elicit any medically related changes in their well-being. They will also be asked if they have been hospitalized, had any accidents, used any new medications, or changed concomitant medication regimens (both prescription and over-the-counter medications).

In addition to subject observations, AEs will be documented from any data collected on the AE page in the eCRF (eg, laboratory values, physical examination findings, and ECG changes) or other documents that are relevant to subject safety.

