6.2.3 Vital Sign Measurements

All vital signs will be measured after the subject has been in the seated position for at least 5 minutes. Vital signs will include systolic and diastolic blood pressure, pulse rate, respiratory rate, and body temperature.

Single Dose (Part 1):

Vital signs will be measured at screening and check-in; prior to aramchol dosing; 4, 12, and 24 hours after dosing; Days 3 and 4; prior to discharge on Day 8 (healthy subjects) or Day 11 (hepatically impaired subjects); and at EOS.

Multiple Dose (Part 2):

Vital signs will be measured at screening and check-in, prior to the AM aramchol dosing on Day 1; 4 hours after the AM dose on Days 1 through 12; prior to discharge on Day 13; and at EOS.

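### Part 1 adverse events are collected over the same period in all groups, but in-clinic surveillance lasts 10 post-dose days in impaired subjects and 7 in controls, and the TEAE summary has no common onset window

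*Combined protocol and SAP*

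**What the plan says.** **Analysis.** Section 7.3.2 (Safety Analyses) states: "Treatment-emergent AEs will be summarized by hepatic condition and overall, as well as by severity and relationship to study drug". It gives no time window. In section 6.2.1.1 a treatment-emergent event is "any event not present before exposure to study drug or any event already present that worsens in intensity or frequency after exposure", so the definition has a start but no end.

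**Collection period.** Section 6.2.1: "Adverse events will be assessed from the time the subject signs the ICF until EOS". The Part 1 schedule (3.1) has a single EOS column, Day 22 (±2), for all cohorts. Its footnote (d) reads: "An EOS visit will occur 11 days after the Day 11 (240-hour) PK blood sample". Section 3 gives one duration for both groups: "The duration of the study, excluding screening, is approximately 23 days".

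**Confinement.** Section 3 keeps Part 1 subjects in the clinic "until discharge on Day 8 for healthy control subjects and on Day 11 for hepatically impaired subjects". Section 6.1 reserves the 192- and 240-hour samples for impaired subjects. The only outpatient visit in schedule 3.1 is EOS, and no telephone contact or diary is listed.

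**Elicitation.** Section 6.2.1.2: "Subjects will be asked a standard question to elicit any medically related changes in their well-being". How often this is asked, in the clinic or after discharge, is not stated.

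**The concern.** From Day 8 to Day 11 impaired subjects are under staff observation and controls are at home. Minor, short-lived events in those days are likely to be noted in the first group. In the second they rest on the subject calling the site or recalling them at EOS, up to two weeks later. A table that pools the whole period by hepatic condition cannot separate this from a real difference.

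Safety in hepatic impairment is the secondary objective (2.2). Section 1.2 frames it as a comparison with healthy subjects, who are the only concurrent reference in the table. Any bias of this kind runs towards more events in impairment. With 8 subjects per cohort, one extra subject moves a cell by 1/8 = 12.5 percentage points.

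The point is confined to Part 1, since section 3 has all Part 2 subjects in the clinic until Day 13.

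**Working it through.** **Inputs from the documents.** Single dose on Day 1; discharge on Day 8 (controls) or Day 11 (impaired) (section 3; 3.1, footnotes b and c); EOS 11 days after Day 11 (3.1, footnote d); 8 subjects per impaired cohort (7.1); half-life about 35 hours for most of the drug and about 3 days for the terminal phase (1.1).

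**Assumptions.** The true event rate *h* per day is constant and the same in both groups. Every in-clinic event is captured. A fraction *c* of outpatient events is captured in both groups. The documents give neither *h* nor *c*, so ranges are shown.

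**1. The plan's own duration.** EOS = Day 11 + 11 = Day 22. Day −1 plus Days 1 to 22, with no Day 0, is 1 + 22 = 23 days, which matches the stated figure.

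**2. Split of follow-up.**

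| | Impaired | Controls |
|---|---|---|
| Post-dose days to EOS | 22 − 1 = 21 | 22 − 1 = 21 |
| In clinic | 11 − 1 = 10 | 8 − 1 = 7 |
| Outpatient | 21 − 10 = 11 | 21 − 7 = 14 |

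The total is equal; only the setting differs. The ±2-day EOS window applies to both groups alike.

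**3. Ratio of recorded events, impaired to control.** (10 + 11c)/(7 + 14c) is 1.00 at c = 1, 1.04 at 0.75, 1.11 at 0.5, 1.21 at 0.25 and 1.43 at 0.

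**4. Subjects with at least one recorded TEAE.** P = 1 − exp[−h × (in-clinic days + c × outpatient days)]. At h = 0.05:

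| c | Impaired | Controls | Ratio | Extra subjects per 8 |
|---|---|---|---|---|
| 1 | 0.650 | 0.650 | 1.00 | 0.00 |
| 0.75 | 0.598 | 0.583 | 1.03 | 0.12 |
| 0.5 | 0.539 | 0.503 | 1.07 | 0.29 |
| 0.25 | 0.471 | 0.408 | 1.15 | 0.50 |
| 0 | 0.393 | 0.295 | 1.33 | 0.79 |

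For example, at c = 0.5 the impaired group has 10 + 5.5 = 15.5 effective days, and 1 − exp(−0.775) = 0.539. Controls have 7 + 7 = 14, and 1 − exp(−0.70) = 0.503. At c = 0 the ratio is 1.39 for h = 0.02 and 1.28 for h = 0.08.

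**5. If the hazard follows drug concentration.** With no outpatient capture and half-life T hours, the event ratio is (1 − 2^(−240/T))/(1 − 2^(−168/T)). For T = 35 it is 0.9914/0.9641 = 1.03. For T = 72 it is 0.9008/0.8016 = 1.12.

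**6. Common window.** From dosing to 168 hours both groups have 7 in-clinic days, so the ratio under equal true rates is 7/7 = 1.00 whatever *c* is.

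**The case against.** The strongest reply is that observation is not unequal. A reader might infer from the discharge days that impaired subjects are simply followed longer, 10 days against 7, and so accrue 1.43 times the events. The documents do not support this: collection runs to the same EOS day in everyone, giving 21 post-dose days in each group. Footnote (d) ties EOS to a Day 11 sample that controls do not have, but the single EOS column and the single duration still place controls at Day 22. This part of the reply stands in full.

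The reply also holds that outpatient capture is not zero. Subjects are told to contact the investigator if symptoms arise (6.2.1.1), and there is an EOS visit at which events are still being collected. Scheduled sources of events are balanced too: vital signs are taken "prior to discharge on Day 8 (healthy subjects) or Day 11 (hepatically impaired subjects); and at EOS", and ECG and laboratory panels follow the same pattern, so the discharge set moves but the count is equal. For drug-related events most exposure is over by 168 hours. All this is fair and keeps the effect small. It does not remove the difference in staff contact between Day 8 and Day 11.

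Finally, the summary is descriptive, all events are listed, comparisons among the impaired cohorts are unaffected, and sections 7.3 and 7.3.1 defer detail to a statistical analysis plan. A listing does let a reader reconstruct onset by hand. But nothing in the present text provides a comparison free of the difference in setting, and the deferred plan is the natural place to add one.

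**Conclusion.** The point holds as a minor weakness of the Part 1 safety summary. The collection period is equal, but in-clinic surveillance is 3 days longer in impaired subjects, and the table does not allow for it. Under equal true rates of 0.05 per day, the ratio of subjects with a TEAE is 1.07 to 1.15 if 50% to 25% of outpatient events are captured, or 0.3 to 0.5 of a subject per cohort of 8. It is smaller if events track drug concentration.

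The ratio of 1.33 (or 1.43 for event counts) should not be read as the expected bias. It requires that no outpatient event is ever recorded, which the contact instruction and the EOS visit make implausible. The rates and capture fractions are assumptions, and the frequency of in-clinic questioning is not stated, so the true size is unknown and could be nil.

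**What to change.** Keep the full-period TEAE table as the main summary. Add to section 7.3.2, or to the statistical analysis plan it defers to, a Part 1 TEAE summary by hepatic condition split by onset: dosing to 168 hours, when all groups are in the clinic, and after 168 hours to EOS. State that the first window is used for the comparison with healthy controls, and note under the second that capture differs by group.

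Time of onset is already recorded (6.2.1.3), so no new data or procedures are needed. The cost is one extra descriptive table. Replacing the main table with one cut at 168 hours would be a poorer trade: it would move late events out of the main comparison in a population where section 1.3 anticipates possible reduced clearance.

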7.4 HANDLING OF MISSING DATA

Plasma concentrations that are below the limit of quantification (BLQ) will be treated as zero for descriptive statistics. Mean BLQ concentrations will be presented as BLQ, and the SD

and CV will be reported as not applicable. Missing concentrations will be excluded from the calculations.

For the PK analysis, BLQ values will be treated as zero with the exception that a BLQ value between 2 quantifiable concentrations will be set as missing. Missing concentrations will be treated as missing from the PK parameter calculations. If consecutive BLQ concentrations are followed by quantifiable concentrations in the terminal phase, those concentrations after BLQ concentrations will be treated as missing.

7.5 INTERIM ANALYSES

No formal interim analyses will be performed in this study.

9. APPENDICES

9.1 APPENDIX 1: LIST OF ABBREVIATIONS

Abbreviation	Term
AE	adverse event
ANOVA	analysis of variance
AUC	area under the plasma concentration versus time curve
AUC _{0-inf}	area under the plasma concentration versus time curve from time 0 extrapolated to infinity
AUC _{0-t}	area under the plasma concentration versus time curve from time 0 to the last quantifiable concentration
AUC _{0-tau, ss}	area under the plasma concentration versus time curve from time 0 to the dosing interval tau at steady state
BLQ	below the limit of quantification
BMI	body mass index
C _{avg, ss}	average plasma concentration at steady state
CFR	Code of Federal Regulations
CL/F	apparent total oral clearance
C _{max}	maximum observed plasma concentration
C _{max, ss}	maximum observed plasma concentration at steady state
C _{min, ss}	minimum observed plasma concentration at steady state
CV	coefficient of variation
ECG	electrocardiogram
eCRF	electronic case report form
EOS	end of study
FDA	Food and Drug Administration
ICF	informed consent form
ICH	International Council for Harmonisation
IRB	institutional review board
k _e	elimination rate constant
MedDRA	Medical Dictionary for Regulatory Activities
NASH	nonalcoholic steatohepatitis
PK	pharmacokinetic(s)
QTcF	QT corrected for heart rate using Fridericia's formula
SAE	serious adverse event
SD	standard deviation
t _{1/2}	apparent terminal phase half-life
T _{lag}	time to the first measurable plasma concentration
T _{max}	time to reach maximum observed plasma concentration
T _{max, ss}	time to reach maximum observed plasma concentration at steady state
T _{min, ss}	time of minimum observed plasma concentration at steady state
V _z /F	apparent volume of distribution

9.2 APPENDIX 2: STUDY GOVERNANCE

9.2.1 Data Quality Assurance

This study will be conducted using the quality processes described in applicable procedural documents. The quality management approach to be implemented will be documented and will comply with current International Council for Harmonisation (ICH) guidance on quality and risk management. All aspects of the study will be monitored for compliance with applicable government regulatory requirements, current Good Clinical Practice, the protocol, and standard operating procedures. The monitor will maintain current personal knowledge of the study through observation, review of study records and source documentation, and discussion of the conduct of the study with the investigator and staff. Electronic CRFs and electronic data capture will be utilized. The electronic data capture system is validated and compliant with US Title 21 CFR Part 11. Each person involved with the study will have an individual identification code and password that allows for record traceability.

Important protocol deviations, should they occur during the study, will be presented in Section 10.2 of the clinical study report.

9.2.2 Investigator Obligations

The following administrative items are meant to guide the investigator in the conduct of the study and may be subject to change based on industry and government standard operating procedures, working practice documents, or guidelines. Changes will be reported to the IRB but will not result in protocol amendments.

9.2.2.1 Confidentiality

All laboratory specimens, evaluation forms, reports, and other records will be identified in a manner designed to maintain subject confidentiality. All records will be kept in a secure storage area with limited access. Clinical information will not be released without the written permission of the subject (or the subject's legal guardian), except as necessary for monitoring and auditing by the sponsor, its designee, the FDA, or the IRB.

The investigator and all employees and coworkers involved with this study may not disclose or use for any purpose other than performance of the study, any data, record, or other unpublished, confidential information disclosed to those individuals for the purpose of the study. Prior written agreement from the sponsor or its designee must be obtained for the disclosure of any said confidential information to other parties.

9.2.2.2 Institutional Review

Federal regulations and ICH guidelines require that approval be obtained from an IRB before participation of human subjects in research studies. Before study onset, the protocol, ICF, advertisements to be used for the recruitment of study subjects, and any other written information regarding this study that is to be provided to the subject or the subject's legal guardian must be approved by the IRB. Documentation of all IRB approvals and of the IRB compliance with the ICH harmonised tripartite guideline E6(R2): Good Clinical Practice will be maintained by the site and will be available for review by the sponsor or its designee.

All IRB approvals should be signed by the IRB chairman or designee and must identify the IRB name and address, the clinical protocol by title or protocol number or both, and the date approval or a favorable opinion was granted.

